Endpoints:	
Primary Endpoint: Change from baseline to 48 weeks (or last available date) in United Multiple System Atrophy Rating Score (UMSARS) total score compared with described progression rates in historical controls. We will assume that patients receiving sirolimus will have a change of 4 points less than those reported in natural history studies (see statistical section).
 
Secondary Endpoints:
 
 1. Change from baseline to 48 weeks (or last available date) in UMSARS-2 subscale score. We will assume that patients receiving sirolimus will have a change of 2 points less than those reported in historical controls. 2. Change from baseline to 48 weeks (or last available date) in UMSARS-1 subscale score. We will assume that patients receiving sirolimus will have a change of 2 points less than those reported in historical controls. 3. Magnetic resonance changes using dedicated algorithms to evaluate rate of change in diffusivity of defined areas of brain from baseline to 48 weeks. 4. Changes in retinal nerve fiber layer using optical coherence tomography from baseline to 48 weeks. 
Exploratory outcome
 
 1. Change in plasma biomarkers (exosomal alpha-synuclein particle concentration) from baseline to 48 months.

Study Population:	A total of 56 patients with multiple system atrophy will be randomized (42 to active agent and 14 to placebo)

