5.5 STRATEGIES FOR RECRUITMENT AND RETENTION

Patients with MSA will be recruited from those that we are currently following at the NYU Dysautonomia Center. Our Center currently follows approximately 100 patients with MSA. In addition, we are in close contact with MSA patients advocacy groups (e.g. *Multiple System Atrophy Coalition*) and will collaborate closely with them in order to disseminate information about the trial and increase the likelihood of recruitment, by means of e-mail blast or letter. The recruitment e-mail/letter to be sent to patients with MSA is attached as an appendix. Any recruitment e-mail or letter to be used in this trial will be submitted to the IRB for approval prior to use.

We expect to screen an average of 8 patients per month and accruing an average of 3 patients per month. At this predicted rate, we expect to complete enrollment of the subjects (n=56) within 24 months with patients recruited only at the NYU Dysautonomia Center. A special effort will be made to include women and minorities.

A screening and enrollment log to record the consent and screening of all subjects and the outcome of each screening will be maintained. The log will provide a comprehensive list of all subjects who were screened for eligibility as well as consented, including the screened failures, the reasons for ineligibility, and reasons for nonparticipation of eligible subjects. This information will be collected centrally, will be included in the Essential Documents Binder, and will be used to enhance subject recruitment efforts.

The principal investigators or co-investigators will approach patients with MSA during a routine clinic visit to inquire whether they would be interested in being enrolled in this clinical trial. If so, patients will be given the consent form. The subject and family will be given enough time to read the informed consent in a quiet room to maintain privacy. The principal investigators, co-investigator or clinical study manager will explain the design of the study, discuss it with the patient and answer any questions or concerns. If the patient is satisfied by the responses of the investigators, the principal investigator will ask the patient to sign the consent form before entering the study. The original signed form will be kept within the study files, and the patient and family will be given a copy.

Screening procedures will include demography, medical history, inclusion and exclusion criteria

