9.2 SAMPLE SIZE DETERMINATION

This study is a randomized, double blind placebo-controlled futility trial in which the primary outcome measure value (UMSARS total score) in a cohort of patients with MSA taking active agent will be compared to a known value from historical controls previously published in the literature. The primary outcome measure was used to calculate the sample size.

The primary statistical analysis will involve a comparison of the mean absolute difference in the active sirolimus group with a pre-specified fixed value, constituting a 4-point reduction in the expected mean increase in the UMSARS total score over 48 weeks without treatment. The expected mean increase in total UMSARS outcomes were obtained from the *U.S. Natural History Study of MSA* (n=96) (39), that reported that the total UMSARS score at 12 months increased a mean of 7.5 (SD: 8.4) absolute points from baseline. Also data from a phase III double-blind placebo-controlled 12-month clinical trial with rifampicin in MSA performed in the U.S. (40) (which was found to be ineffective to slow the progression of the disease) showed that in patients taking placebo (n=50) the total UMSARS score at 12 months increased a mean of 10.8 (SD: 10.7) absolute points from baseline. A weighted analysis of these two populations showed the pooled total UMSARS score at 12-months in patients with MSA in large studies performed in the U.S. had increased a mean of 8.6 (SD: 9.2) points from baseline.

Also, recent studies (38) have determined that the minimally clinically important difference (MCID) in the total UMSARS score is 3.5 points after 48-weeks from baseline.

Taking into consideration this MCID, for this trial, we will assume a promising difference in the UMSARS total score of 4 points between those taking active agent and the historical controls. Specifically, our null hypothesis is that patients receiving sirolimus will have a UMSARS total score progression of only 4.6 points at week 48 higher than baseline, compared to a progression of 8.6 points at week 48 from baseline reported in historical controls from natural history studies and placebo-controlled trials of MSA. Our alternate hypothesis is that sirolimus will be futile to slow the progression of the disease in patients with MSA. The statistical definitions are as follows:

$H_0: \theta_E - \theta_p \leq 4$ where $\theta_p = 8.6$ points increase at week 48 from baseline described in historical controls

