$H_0: \theta_E \leq 4.6$ points increase at week 48 from baseline

$H_1: \theta_E > 4.6$ points increase at week 48 from baseline

Therefore, assuming an alpha of 0.05, and a power of 0.8 (one sided, as patients with MSA have not been reported to improve spontaneously) to detect a progression of 4.6 points (i.e., 8.6 minus 4) in the UMSARS total score after 48-weeks from baseline we will need to enroll 38 patients in the active agent arm. Anticipating a 10% for dropouts rate, we will need to enroll 42 patients in the active agent arm.

This trial will include a placebo group to facilitate blinding in a 3:1 proportion. However, statistical comparisons for the primary and secondary efficacy outcome measures will be performed between the active agent arm and the historical controls. We will therefore enroll 14 patients in the placebo arm.

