9.4.2 ANALYSIS OF THE PRIMARY EFFICACY ENDPOINT

The primary outcome endpoint (UMSARS total score) will be analyzed by comparing the mean decline in total UMSARS score in the active sirolimus group (UMSARS total score at week 48 minus UMSARS total score at baseline) with the pre-specified fixed value of 8.6 (SD: 9.2) using a one-sample t-test. If the difference between the fixed value of 8.6 minus the UMSARS total score in the active sirolimus group is 4 or less, the null hypothesis will be rejected, indicating futility.

Missing data will be addressed by using a regression-based multiple imputation model (78)

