9.4.5 PLANNED INTERIM ANALYSES

Interim efficacy analysis will be performed when 24 patients have completed the trial.

If the efficacy pre-specified criteria are fulfilled, the trial will be stopped for overwhelming efficacy. These pre-specified criteria are:

- The average increase in the total UMSARS score is 4 points or less from baseline to week 48 in patients taking active agent – OR –

- The average increase in the total UMSARS score from baseline to week 48 in patients taking active agent is significantly lower than in patients taking placebo with a $P < 0.001$.

If the futility pre-specified criteria are fulfilled the trial will be stopped for futility. These pre-specified criteria are:

- The average increase in the total UMSARS score is at least 7 points or more from baseline to week 48 in patients taking active agent - OR –
- The average increase in the total UMSARS score from baseline to week 48 in patients taking active agent is significantly higher than in patients taking placebo with a $P < 0.001$.

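### Section 9.4.5 can stop the trial after 24 completers without saying whether the 25–32 unfinished participants are followed or how they enter the primary analysis, and the synopsis and Section 9.4.2 disagree on how to score them

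*Combined protocol and SAP*

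**What the plan says.** Section 9.4.5 sets an interim analysis at 24 completers, arms combined. The trial stops for efficacy if the mean UMSARS increase on sirolimus is 4 or less. It stops for futility if that mean is 7 or more: "If the futility pre-specified criteria are fulfilled the trial will be stopped for futility". Either stop can also be triggered by P<0.001 against placebo. Nothing is said about participants who have not yet reached week 48. Section 10.1.2 adds only that participants will be told of changes to their visits.

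Two statements could apply to their data:

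- The synopsis defines the primary endpoint as "Change from baseline to 48 weeks (or last available date").
- Section 9.4.2 analyses "UMSARS total score at week 48 minus UMSARS total score at baseline" and handles missing data by regression-based multiple imputation. Section 3 also defines the endpoint at week 48 only.

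Section 9.3 limits the analysis to randomized participants with at least 3 months of study drug. On accrual, Section 5.5 states "We expect to screen an average of 8 patients per month and accruing an average of 3 patients per month", and also that all 56 will be enrolled within 24 months.

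**The concern.** The interim falls about when enrolment ends, so a stop mainly cuts follow-up short; it saves little recruitment. UMSARS rises with time. A change measured over 3 to 11 months is therefore smaller than a 48-week change even if the drug does nothing. Comparing it with the 48-week threshold of 4.6 biases the result toward non-futility.

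The plan does not say which of its two statements governs a stopped trial, so the choice could be made after the data are seen. The result matters: the synopsis says rejection of the null will discourage a phase III trial, and non-futility will strongly support one. A trial stopped for futility should not be able to report a non-futile primary result because of how unfinished participants were scored.

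**Working it through.** **Planning value.** Section 9.2 pools a natural history cohort (n=96), which "increased a mean of 7.5 (SD: 8.4) absolute points from baseline", with a placebo arm (n=50), which "increased a mean of 10.8 (SD: 10.7) absolute points from baseline".

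- Mean: (96×7.5 + 50×10.8)/146 = 8.63
- SD, weighted by n: (96×8.4 + 50×10.7)/146 = 9.19

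These reproduce the stated 8.6 and 9.2. The null boundary is 8.6 − 4 = 4.6, tested one-sided at 0.05. The stated 38 does not reproduce at power 0.80 (a one-sample t-test needs 35). At n=38 power is 0.84, so the stated size is conservative; that is a separate matter.

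**Chance of stopping.** At 3:1, 24 completers means about 18 on sirolimus (assumed). SE = 9.2/√18 = 2.17. The placebo criteria are ignored; they can only add to these figures.

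| True mean | P(mean ≤ 4) | P(mean ≥ 7) | Stop |
|---|---|---|---|
| 4.6 | 0.391 | 0.134 | 0.525 |
| 5.5 | 0.245 | 0.245 | 0.489 |
| 6.6 | 0.115 | 0.427 | 0.542 |
| 8.6 | 0.017 | 0.770 | 0.787 |

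**Unfinished participants.** Week 48 is 336 days, about 11.0 months.

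- At 3 per month, the 24th participant enters at 24/3 = month 8 and finishes at about month 19.0. All 56 are enrolled by 56/3 = month 18.7. Unfinished: 56 − 24 = 32, of whom 0.75×32 = 24 are on sirolimus. About 18 of these have at least 3 months of drug.
- At 56/24 = 2.33 per month, the 24th finishes at 10.3 + 11.0 = month 21.3, when about 49.8 are enrolled. Unfinished: about 25.8, of whom about 19 are on sirolimus and about 15 have 3 months of drug.

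The Section 9.3 population is therefore 18 + 18 = 36 or 18 + 15 = 33. Without further follow-up, multiple imputation would have to supply 50% or 45% of week-48 values.

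**Mean for an inert drug (true 8.6, linear progression assumed), 3 per month.**

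- Last scheduled visit carried: the 18 unfinished participants average half the interval. (18×8.6 + 18×0.5×8.6)/36 = 6.45.
- UMSARS taken at the stop: they average about 0.64 of the interval. (18×8.6 + 18×0.64×8.6)/36 = 7.05.

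The slower accrual gives about 6.6 and 7.1.

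**Chance that the final test fails to declare futility, given a futility stop (true 8.6).** The simulation used a random slope plus visit error with total 48-week SD 9.2, residual share 10%, 30% or 60%, the 3-month rule, no dropout, and the interim read when the 24th participant finishes.

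| Data used | Not futile, t-test against 4.6 |
|---|---|
| Last scheduled visit carried | 51–58% |
| UMSARS at the stop | 31–42% |
| 18 completers only | about 29% |
| All followed to week 48 | 8–11% |

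A simpler variance model for partial follow-up gave 36–46% for the second row. Reading the interim up to a month later raises the carried-visit mean to as much as 6.8 and lowers the first row, to about 45% in the slower-accrual case with a 30% residual share.

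The completers-only figure can be checked by hand. With n=18 the test rejects when the mean exceeds 4.6 + 1.740×2.17 = 8.37, but the trial stops at 7. P(7 ≤ mean < 8.37)/P(mean ≥ 7) at true mean 8.6 is about (0.458 − 0.230)/0.770 = 0.30, in line with the simulated 29%.

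**Alternative decision rule.** Section 9.4.2 also says futility is declared when 8.6 minus the sirolimus mean is 4 or less, that is, when the mean is at least 4.6. Under that sentence, last-available scoring gives a non-futile result after a futility stop at most about 5% of the time.

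**The case against.** Several stronger readings are tempting, and the documents do not support them.

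- *Unfinished participants can never reach week 48.* The text is silent on this. For an individual who stops drug early, Sections 4.1 and 7.1 continue follow-up. These rules are not extended to a stopped trial, but nothing forbids doing so.
- *The plan would score them at their last visit.* For the primary endpoint, that wording stands only in the synopsis. The statistical section specifies week 48 and multiple imputation. The defect is an unresolved conflict.
- *A contradictory result would occur more than half the time because of last-available scoring.* That figure needs the last scheduled visit carried. Sections 4.1 and 7.1 already list a UMSARS when an individual stops drug early; applied at a trial stop, it lowers the figure to 31–42%. About 29% arises from the completers alone, because the cut-off of 7 lies below the 18-patient rejection point of 8.37. Under the point-estimate sentence the contradiction nearly disappears. Section 9.4.2 also names a t-test, and Section 9.2 sets "assuming an alpha of 0.05, and a power of 0.8 (one sided, as patients with MSA have not been reported to improve spontaneously"), so which rule governs is unclear.
- *A stop is always more likely than not.* It dips to about 49% near a true mean of 5.5. At 4.6, most stops are for efficacy (39.1% against 13.4%).

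It is also fair to say that multiple imputation could use the scheduled month 3, 6 and 9 scores, so a mixed model is not the only sound answer.

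What remains is the silence on a likely event, the conflict between the two statements, and the downward bias if the synopsis wording is followed.

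**Conclusion.** The concern holds as a gap and a conflict; it is not an error certain to occur. A stop is likely at both of the plan's own values (about 52% at 4.6, 79% at 8.6), and about 19–24 sirolimus participants would then be unprovided for. Following the synopsis wording would lower an inert drug's mean from 8.6 to about 6.5–7.1 against a full 48-week threshold. It would raise the chance of a non-futile t-test after a futility stop to 31–58%, against 8–11% with complete follow-up. Part of that excess comes from the interim cut-off and not from the scoring rule.

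These sizes rest on 18 treated completers, SD 9.2, uniform accrual, linear progression, no dropout, and the t-test against 4.6 as the decision rule. The documents do not establish linearity. This should be settled before the interim; confidence in the exact sizes is medium.

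**What to change.** 1. Delete the last-available-date alternative from the primary endpoint in the synopsis, and from the UMSARS-1 and UMSARS-2 endpoints for consistency. Or state that such changes are never used as week-48 changes for participants cut short by an interim stop.
2. State in Section 9.4.5 whether UMSARS follow-up continues after a stop.
3. State in Sections 9.4.5 and 9.4.2 that, after a stop, the primary estimate is the week-48 change from one prespecified longitudinal analysis of all scheduled UMSARS in the sirolimus arm, tested one-sided against 4.6. This can be a mixed model on time since baseline, or the planned multiple imputation using the month 3, 6 and 9 scores and the early-termination UMSARS. Name one.
4. In the same edit, say whether the t-test or the point-estimate sentence in Section 9.4.2 decides futility.

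The cost is wording and one analysis of visits already scheduled. The downside is reliance on an assumed shape of progression, which can be checked in the completers. This does not remove the mismatch between the cut-off of 7 and the 18-patient rejection point, but it replaces a choice made after the fact with a stated one.

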9.4.3 ANALYSIS OF THE SECONDARY ENDPOINT

In order to maintain the overall type I error at the 0.05 level, an hierarchy will be employed as follows: If the primary endpoint is found to be significant at a significance level of 0.05, then the first key secondary endpoint will be tested; if this endpoint is found to be significant in a significance level of 0.05, then the second key secondary endpoint will be tested and so on. The key secondary endpoints and their order in the hierarchy are:

UMSARS sub-scores: The secondary outcome endpoint (UMSARS-1 and UMSARS-2 scores) will be analyzed by comparing the mean decline in total UMSARS-1 and UMSARS-2 score in the active sirolimus group (UMSARS-1 and UMSARS-2 at week 48 minus UMSARS-1 and UMSARS-2 at baseline) with the pre-specified fixed value of 4.5 (SD: 5.5) in each score using a one-sample t-test.

Brain magnetic resonance imaging: The secondary outcome endpoint (putaminal diffusivity) will be analyzed by comparing the mean increase in Trace(D) score in the active sirolimus group (Trace(D) score at week 48 minus Trace(D) score at baseline) with the pre-specified fixed value of 0.07 ($\times 10^{-3}$ mm²/sec) using a one-sample t-test.

Retinal optical coherence tomography: The secondary outcome endpoint (retinal nerve fiber layer

thickness) will be analyzed by comparing the mean decline in RNFL thickness in the active sirolimus group (RNFL at baseline minus RNFL at week 48) with the pre-specified fixed value of 3.7 μm using a one-sample t-test.

Concentration of exosomal αSyn particles: This exploratory outcome endpoint will be analyzed by comparing the mean change in αSyn exosomal particles concentration (week 48 minus baseline) in the active sirolimus group with the placebo group.

In all cases missing data will be addressed by using a regression-based multiple imputation model (78)

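### The interim futility stop at a raw mean of 7 points has no error control: with about 18 treated it discards a drug exactly at the 4.6-point target 13% of the time, against the one-sided 0.05 set in section 9.2

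*Combined protocol and SAP*

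**What the plan says.** The protocol contains the whole statistical plan.

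- **Timing (9.4.5):** "Interim efficacy analysis will be performed when 24 patients have completed the trial". The split by arm is not given.
- **Consequence (9.4.5):** "If the futility pre-specified criteria are fulfilled the trial will be stopped for futility".
- **First futility criterion (9.4.5):** "The average increase in the total UMSARS score is at least 7 points or more from baseline to week 48 in patients taking active agent". A second criterion, joined by OR, is that the active arm is worse than placebo at P<0.001.
- **Hypotheses (9.1, 9.2):** H0 is a mean increase on sirolimus of at most 4.6 points (8.6 minus 4); H1 is more than 4.6. Section 4.1 says that rejecting H0 means the drug is considered futile.
- **Error rates and size (9.2):** "assuming an alpha of 0.05, and a power of 0.8 (one sided, as patients with MSA have not been reported to improve spontaneously"), and "we will need to enroll 38 patients in the active agent arm" before a 10% dropout allowance raises this to 42.
- **Historical value (9.2):** the pooled total score "had increased a mean of 8.6 (SD: 9.2) points from baseline".

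No section gives a spending function, an adjusted final critical value or operating characteristics for the interim look. Section 10.1.6 gives the medical monitor a general power to recommend termination but does not mention this rule.

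**The concern.** In a conventional trial a futility stop costs power and leaves the type I error alone. Here the hypotheses are reversed, so every early futility stop is a rejection of H0 and spends alpha. A raw cut-off of 7 lies only 2.4 points above the target, and the standard error of the mean on about 18 patients is roughly 2.2 points. A drug that slows progression by exactly the amount the sponsor calls promising could therefore be discarded at the interim by chance, much more often than the 5% the design allows. The second criterion cannot restrain the first, because meeting either one is enough.

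**Working it through.** **The plan's own figure.** The one-sample normal formula n = (9.2 × (1.645 + 0.842)/4)² gives 32.7, so 33; the exact one-sample t-test gives 35. The stated 38 is not reproduced but is on the safe side: power at 38 is 83.8%. The interim calculation below does not use 38.

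**Inputs.**

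- Cut-off 7 and 24 completers: 9.4.5.
- Target 4.6 and SD 9.2: 9.2.
- SD range 8.4 to 10.7: the natural history study and the rifampicin placebo arm quoted in 9.2.
- Number treated at the interim: 24 × 3/4 = 18, an assumption from the 3:1 allocation. A range of 16 to 24 is shown; 24 means that every completer was on sirolimus.

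**Step 1: false stop at the interim.** P = 1 − Φ((7 − 4.6)/(SD/√n)). With n = 18 and SD 9.2, SE = 9.2/√18 = 2.168, z = 2.4/2.168 = 1.107 and P = 13.4%.

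| Treated | SD 8.4 | SD 9.2 | SD 10.7 |
|---|---|---|---|
| 16 | 12.7% | 14.8% | 18.5% |
| 18 | 11.3% | 13.4% | 17.1% |
| 24 | 8.1% | 10.1% | 13.6% |

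Every cell exceeds 5%. At SD 9.2 the cut-off would reach 5% only with (1.645 × 9.2/2.4)² ≈ 40 treated, more than the 38 planned for the final analysis.

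**Step 2: strength of evidence at the cut-off.** An observed mean of 7.0 gives t = 1.107 on 17 df, one-sided p = 0.14 against 4.6. With 24 treated, t = 1.278 on 23 df and p = 0.11. The mean needed for an unadjusted one-sided p of 0.05 is 4.6 + 1.687 × 1.492 = 7.12 at n = 38, but 8.37 at n = 18. So 7 is close to the critical mean for the full sample, applied to 18/38 = 47% of it.

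**Step 3: whole trial.** Simulation of 400,000 trials with 38 active patients, both raw-mean stops of 9.4.5 (7 or more for futility, 4 or less for efficacy), then a final one-sided 0.05 t-test against 4.6. The placebo P<0.001 criteria were not simulated.

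| True mean | Quantity | With interim | Without interim |
|---|---|---|---|
| 4.6 | declared futile (wrongly) | 15.1% | 5.0% |
| 8.6 | declared futile (correctly) | 89.4% | 83.8% |

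Over the input range of Step 1 the 15.1% runs from 10.0% to 19.9%. With the 7-point stop alone it is 15.3%, so that stop is the cause. At a true mean of 8.6, 77% of trials stop for futility at the interim.

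**The case against.** **A phase II screen can accept a higher false-futility rate.** The excess is greatest exactly at 4.6: with 18 treated and SD 9.2 the interim stop falls to 8.3% at a true mean of 4.0 and 3.3% at 3.0. In return, a useless drug is discarded 89% of the time instead of 84%. This is a fair trade to argue for, but the plan states 0.05 and argues for nothing else.

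**The 15% against 5% contrast assumes a final test the plan does not write.** This stands. Section 9.4.2 rejects on a point estimate: "If the difference between the fixed value of 8.6 minus the UMSARS total score in the active sirolimus group is 4 or less". Taken literally, that gives about 50% false futility at 4.6 without the interim and 43% with it; the interim lowers the figure because the 4-point stop fires about 39% of the time. That rule is a separate error. The 13.4% does not depend on it, and correcting 9.4.2 alone leaves the interim above 0.05.

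**Section 9.4.3 does not extend to the interim.** Its phrase "In order to maintain the overall type I error at the 0.05 level" introduces the secondary-endpoint hierarchy and says nothing about interim looks. Agreed; the benchmark is the alpha in 9.2, which is sufficient.

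**The interim comes late.** At the 3 patients per month expected in 5.5, all 56 are enrolled by about month 19 (56/3 = 18.7). The 24th patient enters at month 8 and completes about 11 months later, also about month 19 (no dropout). A stop would save follow-up and exposure but little or no enrolment. This weakens the case for an aggressive early cut-off and makes the fix cheaper.

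**Conclusion.** The concern holds. The 7-point stop is binding, and by itself it gives a false-futility rate of 13.4% at the target, more than twice the one-sided 0.05 in section 9.2. This rests on about 18 treated completers (inferred), SD 9.2 and normally distributed means. The conclusion does not depend on those exact values: the lowest rate, with all 24 on sirolimus and SD 8.4, is 8.1%. The trial-wide figure of about 15% additionally assumes that 9.4.2 is corrected to a one-sided 0.05 t-test against 4.6 with 38 analysed. This must be fixed, because the stated alpha is not the alpha of the plan as written.

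**What to change.** Choose one of the following and state its operating characteristics in 9.4.5. All are protocol wording and need no extra patients.

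**(a) Spend alpha.** Replace the 7-point cut-off with a one-sided t-test of H0 (mean at most 4.6) under a named spending function, with an adjusted final critical value so that total one-sided alpha is 0.05. At 18/38 information and SD 9.2, without the 4-point stop:

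| | O'Brien-Fleming-type | Pocock-type |
|---|---|---|
| Interim p below | 0.0044 | 0.030 |
| Approximate interim mean (t; normal theory) | 11.0; 10.3 | 9.0; 8.7 |
| Final p below | 0.049 | 0.030 |
| Simulated total alpha | 0.050 | 0.051 |
| Interim stop if true mean is 8.6 | 17% | 45% |
| Power at 8.6 | 84% | 79% |

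State the boundary as a p-value or t value, since the equivalent mean depends on the observed SD and number treated. The cost is fewer early stops of a useless drug (77% now); power stays near the planned 80%.

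**(b) Keep 7 and declare it.** Restate the overall one-sided false-futility rate as about 15% in 9.2 and justify it for a phase II screen. The cost is that about 1 in 7 drugs exactly at target is discarded.

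**(c) Drop the efficacy and futility look** and keep safety monitoring. Alpha is then 5% and power 83.8% at 38. The cost is the loss of early stopping, which is small given the accrual timing.

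All three also require the final rule in 9.4.2 to be rewritten as a test of 4.6. If the interim is kept, relabel the 4-point efficacy stop as early non-futility, and reconcile the placebo-based P<0.001 criteria with 4.1 and 4.2, which say that the placebo arm is not a comparator for the active arm.
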